A mixed methods process evaluation will explore acceptability, feasibility and contextual factors impacting intervention delivery guided by the Consolidated Framework for Implementation Research. Qualitative data collection during the first 4 weeks will be curtailed to minimise exposure of research staff completing qualitative interviews (high risk for COVID-19 transmission) and will be limited to observation of CHW training and up to 5 initial CHW household assessments. We will explore the feasibility of recording and analysing telephone interactions between CHWs and households. Once a household has been determined to be COVID-19 free (2 weeks after last symptoms in a diagnosed person) trained qualitative interviewers will conduct interviews with patients, household contacts and caregivers. These in-depth interviews will be limited to a purposive sample of 5 households per group. CHWs and community leaders will also be interviewed.

Assessing SARS-CoV-2 transmission: The research team will conduct SARS-CoV-2 testing with household contacts at baseline and weekly for 1 month. SARS-CoV-2 transmission will be monitored using nasopharyngeal nostril swabs for SARS-CoV-2 GeneXpert PCR and antibody COVID-19 IgG/IgM Rapid serology assays. Nasopharyngeal samples will be collected in a well-ventilated sputum collection space and staff will have adequate protective equipment. Venepuncture will be used to obtain dried blood spots. The test results will be delivered telephonically to household contacts within 24 hours of the test. HHC will complete a daily symptom checklist and symptom data will be collated weekly by the research team. Six months after a positive SARS-CoV-2 antibody, the study nurse will visit the participant household to conduct SARS-CoV-2 serology to assess for the presence of antibodies.

Eligibility of index case:

Inclusion:

Individual >12 years

Able to give assent if <18 years with parental/guardian consent

Able to give consent > 18 years

Self-isolating at home at the time of COVID diagnosis

Exclusion:

<12 years

Unable to give consent

Eligibility of HHC

Inclusion:

Living in the same household as index case

Able to give assent if 12-17 years with parental/guardian consent

Able to give consent \geq 18 years

Exclusion:

Unable to give consent

Table 2: Study procedures

Study participant	Procedure	Baseline	Week	Week	Week	Week
			1	2	3	4
Index						
	ICF		x			
	Demography survey		x			
	Symptom check	x		x	x	x
	Follow up surveys	x		x		x

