8.3. The proportion of index patients and HHC that showed improved psychosocial functioning in the intervention arm as compared to the enhanced usual care (EUC) arm. 10	
8.4. The association between the time to transmission and clinical symptoms of the index cases.....	10
8.5. The symptomatic/asymptomatic ratio among transmitted SARS-CoV-2 in household contacts	10
8.6. The incidence of SARS-CoV-2 transmitted to HHC of the index COVID19 cases over a 4 week period, stratified by COVID-19 wave.....	10
8.7. Analysis of household exposure to SARS-CoV-2 at baseline using the baseline serology result, and development of antibodies using the serology result during follow-up. 10	
8.8. Process Evaluation Analysis.....	11

1. ***INTRODUCTION***

This Statistical Analysis Plan (SAP) describes the statistical methods to be used during the analysis and reporting of data collected for the TRACE study. This SAP should be read in conjunction with the Study Protocol (dated 15 December 2020), Case Report Forms (CRFs, Final Versions, dated 4 November 2020) and Data Management Plan (DMP, dated 18 June 2020).

2. ***OBJECTIVES OF THE STUDY***

2.1. **Primary objectives**

1. To measure frequency and timing of transmission of SARS-CoV-2 to household contacts.
2. To investigate the effect of an intensive infection mitigation intervention (STOPCOV) administered by lay health care workers on the household transmission of SARS-CoV-2.

[figure not shown]
2.2. **Secondary objectives**

1. To investigate the effect of the STOPCOV intervention on clinical outcomes and psychosocial functioning
2. To investigate the difference in transmission of SARS-CoV-2 to HHC stratified by COVID-19 wave (first or second wave)
3. To describe the household exposure to SARS-CoV-2 at baseline using the baseline serology result, and development of antibodies using the serology result during follow-up.
4. To assess acceptability, feasibility and contextual factors impacting intervention delivery (process evaluation), specifically:
 - a. To understand the acceptability and feasibility of the STOPCov intervention.
 - b. To understand how context shapes implementation of the STOPCov intervention at the level of households and individuals.
 - c. To provide explanations for observed trends in the trial findings.
 - d. To generate theoretical generalisations of how to optimise wider implementation of the STOPCov intervention to other households to reduce transmission of COVID-19.

3. ***DESIGN OF THE STUDY***

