Overview

A cluster randomised controlled study with longitudinal follow up of SARS-CoV-2 infection in 120 households which have newly diagnosed positive cases. The index cases and their HHC will be invited and enrolled after informed consent. Baseline surveys and SARs-CoV-2 screening (PCR and IgM/IgG serology) and then weekly SARs-CoV-2 screening (PCR and serology) of HHC will occur at 0, 1, 2, 3 and 4 weeks. The households will be randomized to an intensified COVID19 infection mitigation intervention (n=60) administered by CHWs vs the standard messaging (n=60). Please see Figure 1 for a schematic overview of the study design.

EUC = enhanced usual care

Figure 1: Flow chart and schematic overview of the study design.

Sample Size Determination

We calculated the different effect sizes (Table 1). Based on exponential test for comparing hazards, assuming $120*6=720$ subjects, different intraclass correlation coefficients (ICCs) and comparing $R_0=2.5$ (with resulting incidence of 0.208 among 720 subjects) to a reduced R_0 of 0.9 (64% reduction, with resulting incidence of 0.075 among 720 subjects) or 1.25 (50% reduction) or 1.5 (40% reduction).

Table 1: ICC calculations

ICC	R0 2.5 to 0.9	R0 2.5 to 1.25	R0 2.5 to 1.5
	64% reduction	50% reduction	40% reduction
0.05	1.00000	1.00000	0.999944
0.25	1.00000	0.999891	0.991312
0.50	0.999993	0.995042	0.935880
0.75	0.999729	0.972942	0.846222
0.90	0.999033	0.951485	0.792745

Randomization and stratification

After completing consent, households will be randomised in a 1:1 ratio in blocks of 10 (60 households per group; 360 patient and household contacts per group).

Overview of data and data sources for analysis

All data are collected with two individual identifiers: study ID and PID (Western Cape Government health number). The exception is data source #4, which only uses PID.

1. Redcap database
 - a. Baseline survey of index patient and household characteristics (demographics, COVID-19 symptoms, household tracing information, home/dwelling characteristics that impact transmission (size, rooms, ventilation, access to safe water, laundry facilities))
 - b. Uptake of infection control measures at all follow-up contacts (assessment of use of isolation measures and cleaning of household surfaces up to 10 days post case of last diagnosis in household, at 1, 2, 3, 4 weeks).

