 - c. Assessment data of psychosocial functioning (General Health Questionnaire 9 for mood; UCLA Loneliness Scale and a version of the Brief AIDS-Related Stigma scale adapted for COVID-19, at baseline and at week 4);
 - d. Results of serology (pos/neg, no titres) and nasopharyngeal swabs for PCR of HHCs at baseline, and at weeks 1, 2, 3 and 4);
2. Randomisation list
3. Qualitative and quantitative process data on intervention (STOPCOV database)
 - a. Number and duration of calls to households
 - b. transcripts from follow-up calls
 - c. SMS/WhatsApp data
 - d. transcripts from interviews with STOPCov counsellors and intervention/control index and HHC participants
4. Provincial health data(PID; all study participants and household contacts)

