7. ANALYSIS OF PRIMARY STUDY OUTCOMES

7.1. The proportion of SARS-CoV-2 transmitted to HHC of the index COVID19 cases over a 4 week period

SARS-CoV-2 infection in a HHC will be defined as a positive PCR or evolving positive serologic test in a HHC who had a negative PCR or negative serology at baseline. The incidence of SARS-CoV-2 infection in HHC will be calculated as the number of new cases divided by the person time at risk and 95% confidence intervals calculated based on the Poisson distribution adjusted for clustering by household. This incidence as well as the timing to transmission will be analysed using exponential shared frailty models taking the clustering by household into account and allowing for censoring. The start time will be the date of diagnosis of the index case and the event time the date of diagnosis of the HHC using the date of the first positive test based on PCR or serology. Models will include possible confounders including adjustment for baseline values.

7.2. The proportion of transmissions to HHC in the enrolled households of index COVID cases assigned to the infection mitigation intervention arm compared with the households in the enhanced usual care (EUC) arm.

The incidence of SARS-CoV-2 will be estimated for the different study arms and incidence of and timing to SARS-CoV-2 per study arm will be compared by including study arm in the exponential frailty models.

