8.5. The symptomatic/asymptomatic ratio among transmitted SARS-CoV-2 in household contacts

The proportion of symptomatic and asymptomatic transmitted SARS-CoV-2 infections will be calculated, overall, with 95% confidence intervals based on binomial or asymptotic normal distributions.

8.6. The incidence of SARS-CoV-2 transmitted to HHC of the index COVID19 cases over a 4 week period, stratified by COVID-19 wave.

The incidence of SARS-CoV-2 will be compared by COVID-19 wave using exponential frailty models and including an indicator of the wave in the model.

The COVID19 wave will be defined as follows:

- wave 1: date of diagnosis of index case between 1 May and 31 November
- wave 2: date of diagnosis of index case from 1 December onwards

8.7. Analysis of household exposure to SARS-CoV-2 at baseline using the baseline serology result, and development of antibodies using the serology result during follow-up.

Longitudinal weekly prevalence profiles of serology results will be summarized overall and by study arm. These profiles can be analysed using hierarchical mixed effect logistic regression models with both household and HHC as nested random effects. Time to development of antibodies can be analysed using exponential frailty models. Models will include baseline serology results.

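### Baseline household exposure is described by serology alone, so contacts PCR-positive but not yet seropositive drop out of it and can later count as developing antibodies; the baseline PCR should be shown beside it

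*SAP*

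**What the plan says.** SAP 2.2, secondary objective 3, is "To describe the household exposure to SARS-CoV-2 at baseline using the baseline serology result", together with the development of antibodies during follow-up. SAP 8.7 carries the same title: "Analysis of household exposure to SARS-CoV-2 at baseline using the baseline serology result". Its planned output is serological: "Longitudinal weekly prevalence profiles of serology results will be summarized overall and by study arm". It also allows mixed logistic models of the weekly results and frailty models for time to antibodies, and adds: "Models will include baseline serology results". Neither section mentions PCR.

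Both tests are done at week 0. The design overview in SAP section 3 lists "Baseline surveys and SARs-CoV-2 screening (PCR and IgM/IgG serology"), and data source 1d in the same section holds "Results of serology (pos/neg, no titres) and nasopharyngeal swabs for PCR of HHCs at baseline". Protocol Table 1 (Interventions) limits testing to at most 8 contacts per household, aged 12 or older. The Protocol paragraph on assessing transmission specifies "antibody COVID-19 IgG/IgM Rapid serology assays".

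For the primary outcome, SAP 7.1 uses both tests: infection is "defined as a positive PCR or evolving positive serologic test". SAP 4.2 lists the proportion who developed antibodies during follow-up as a secondary outcome.

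**The concern.** SAP 7.1 accepts a positive PCR as infection and expects antibody status to change during follow-up. The plan therefore recognises that a person can be infected before being seropositive. Households enter because of a newly diagnosed case, so some contacts may be in that state at the baseline visit. They are the contacts a serology-only summary leaves out.

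Two things are at stake.

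- **Baseline description.** It omits infections that the study has itself detected at the same visit. It also pools all seropositive contacts, whenever they were infected.
- **Antibody-development outcome.** A contact who was PCR-positive and seronegative at baseline and later seroconverts is a follow-up event. That infection preceded the baseline swab, so neither arm could have prevented it.

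**Working it through.** The plan gives no figure to reproduce. The check is a comparison of texts, followed by an illustration of size.

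**Step 1: how each baseline pattern appears under 8.7 and under a two-test table**

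| Baseline PCR | Baseline antibody | Under 8.7 | What both tests show |
|---|---|---|---|
| + | − | negative; a later seroconversion is an event | current infection, not yet seropositive |
| + | + | positive | PCR-positive at baseline |
| − | + | positive | previously infected, timing unknown |
| − | − | negative; a later seroconversion is an event | no infection detected by either test |

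Rows 1 and 4 are the same under 8.7, as are rows 2 and 3. Baseline serology as a covariate takes the same value in rows 1 and 4, so it cannot separate a seroconversion from an infection already present at baseline from one that follows a later infection. Baseline PCR can.

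**Step 2: possible size at contact level (all inputs assumed except 720)**

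Let a be the share infected before this outbreak (10% to 30%, all assumed still seropositive), b the share of the remainder infected in this outbreak by baseline (10% to 30%), and f the share of those still seronegative (30% to 90%). Both tests are taken as error-free. The 720 subjects come from the SAP sample-size section and serve only as a scale.

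- Infected but seronegative = (1 − a) × b × f.
  - Low: 0.7 × 0.1 × 0.3 = 0.021, or 15 of 720.
  - High: 0.9 × 0.3 × 0.9 = 0.243, or 175 of 720.
- Ever infected = 1 − (1 − a)(1 − b) = 0.37 in both cases. The missed share is 0.021/0.37 = 6% and 0.243/0.37 = 66%.
- Share of seropositives infected before this outbreak = a / [a + (1 − a) × b × (1 − f)].
  - Low (a = 0.1, b = 0.3, f = 0.3): 0.1/0.289 = 35%.
  - High (a = 0.3, b = 0.1, f = 0.9): 0.3/0.307 = 98%.

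**Step 3: direction depends on what exposure means**

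If it means any infection to date, serology alone can never exceed PCR or serology combined. If it means infection in this outbreak, compare the seropositive share, a + (1 − a) × b × (1 − f), with (1 − a) × b:

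- a = 0.3, b = 0.1, f = 0.3: 0.349 against 0.07, so serology overstates.
- a = 0.1, b = 0.3, f = 0.9: 0.127 against 0.27, so serology understates.

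**Step 4: household level (assumed inputs)**

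Take 6 contacts, 20% positive on either test, and independence within households. P(at least one) = 1 − (1 − p)^6.

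| Share of positives detected by PCR only | p by serology | Households with at least one |
|---|---|---|
| 0% (same as either test) | 0.20 | 73.8% |
| 25% | 0.15 | 62.3% |
| 50% | 0.10 | 46.9% |
| 75% | 0.05 | 26.5% |

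Clustering of infection within households would narrow the household gap but would not change the contact-level fall.

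**The case against.** The strongest reply is that objective 3 is a serology objective by design. It pairs baseline serology with later antibody development and leaves PCR-detected infection to SAP 7.1. Every enrolled household has a diagnosed index case, so every household is exposed in the ordinary sense. Contacts who are PCR-positive and seronegative are not lost, since they enter the weekly profiles once they seroconvert. SAP 6.1 already reports the time from the index patient's positive test to enrolment.

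Much of this stands, and it rules out several stronger readings that a reader might infer.

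- **That the SAP classes these contacts as unexposed.** It has no exposed/unexposed rule and does not define household exposure.
- **That the reported exposure is too low.** This holds only if exposure means any infection to date (step 3).
- **That old and new infections cannot be separated.** The assay reads IgM and IgG, and the PCR is in the same database. The SAP does not say whether the two bands are recorded separately, and it plans no use of them.
- **That adding PCR would date every infection.** It would not. A PCR-negative, seropositive contact may have been infected before the index case or within the same household outbreak.

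The reply does not answer the second half of the concern. Seroconverters already PCR-positive at baseline enter the antibody analysis as follow-up events, and only the baseline PCR identifies them.

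**Conclusion.** The point holds as a low-cost improvement to a descriptive secondary objective. It is not a demonstrated error. The text establishes that SAP 2.2(3) and 8.7 use serology alone, that a baseline PCR exists for the same tested contacts, that PCR-positive, seronegative contacts are absent from the measure, and that baseline serology cannot pick them out if they seroconvert.

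The size cannot be determined from the documents. The ranges in steps 2 and 4 rest on assumed prevalences, assumed seronegative shares, error-free tests and, at household level, independence; their width shows how little is known.

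A reader might infer that the primary comparison is biased. The documents do not support that on this ground: SAP 7.1 and 7.2 use their own infection definition, which includes PCR, and do not draw on the measure in 8.7. The gain is a clearer baseline description and a cleaner antibody-development analysis, whichever meaning of exposure was intended.

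**What to change.** 1. In SAP 2.2(3) and 8.7, state what household exposure at baseline means, and report the four-way baseline PCR-by-serology classification per contact and per household, by arm and by wave as defined in 8.6.
2. Label the cells as follows: PCR-positive/antibody-negative, *current infection, not yet seropositive*; PCR-positive/antibody-positive, *PCR-positive at baseline*; PCR-negative/antibody-positive, *previously infected, timing unknown*. The last should not be called infection before the index case.
3. In the 8.7 antibody-development models, include baseline PCR alongside baseline serology, or also show the models without contacts who were PCR-positive at baseline.

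The cost is a wording change, one table and one covariate (or one repeated model). Both results are already collected at the same visit, so no new testing or data capture is needed.

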Aims: Specific Aim 1: To measure frequency and timing of transmission of SARS-CoV-2 to household contacts. The proportion of patients and household contacts who have symptoms vs asymptomatic disease will also be measured. Specific Aim 2: To investigate the effect of an intensive infection mitigation intervention (STOPCOV) administered by lay health care workers on the household transmission of SARS-CoV-2, clinical outcomes and psychosocial functioning.
Design: The study design is a type 2 hybrid cluster (household) randomised controlled trial, with outcomes assessed on index patients and their household contacts (Fig 1). 120 consecutively newly diagnosed index patients (GeneXpert SARS-CoV-2 PCR) and up to 8 household contacts will be invited to participate in the trial as part of the prospective observational study evaluating transmission and symptoms. After completing consent, households will be randomised in a 1:1 ratio in blocks of 10 (60 households per group; 360 patient and household contacts per group).
Study setting and population: Klipfontein is a resource-limited, densely populated, high HIV/TB disease burden areas in Cape Town. Newly diagnosed COVID19 cases will be identified from two sources: screening conducted in DTHF mobile screening units and local public sector clinics working closely with DTHF. Consecutive cases (n=120 cases and households) will be invited to participate in the randomised trial and prospective longitudinal follow up of up to ~6 -8 household contacts. The contacts will be followed up after informed consent to SARS-CoV-2 screening, symptomatic questionnaires weekly up to 1 month.
Study size: We will enrol n=120 SARS-CoV-2 positive and n=~6 their household contacts (n=~720).

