Overall Objective: The overarching objective of this protocol is to understand and mitigate household transmission of SARS-CoV-2 infection in a low income, high-density community setting. Data over an 8-month period will be used to determine the Ro for SARS-CoV-2 infection, the rate of symptomatic disease and the impact of a lay health care worker administered infection mitigation intervention (STOPCOV) in low income, high-density communities in South Africa.

Specific Aim 1: To measure frequency and timing of transmission of SARS-CoV-2 to household contacts. The proportion of patients and household contacts who have symptoms vs asymptomatic disease will also be measured.

Specific Aim 1 Endpoints: SARS-CoV-2 transmission will be monitored using nasopharyngeal swabs for SARS-CoV-2 PCR and serology (IgM/IgG) assays in all HHC weekly for 1 month. Symptom checklists will be completed daily and collated weekly for each HHC.

Specific Aim 2: to investigate the effect of an intensive infection mitigation intervention known as STOPCOV administered by lay health care workers, compared with enhanced usual care, on SARS-CoV-2 household transmission.

Specific Aim 2 Primary Endpoint: The proportion of transmissions to HHC in the households of COVID cases assigned to the infection mitigation intervention arm compared with the households in the enhanced usual care (EUC) arm.

Population and Sample: We will consecutively recruit n=120 SARS-CoV-2 positive index patients 12 years and older. The index patients will be identified from referrals from associated public sector clinic screening in a high-density community in Cape Town. Each household is estimated to have 6-8 occupants. We will invite HHC (n=~6-8) household contacts of each of the index patients (n=~720).

Duration: The study will be conducted for eight months from June 2020 and last until Jan 2021.

[figure not shown]

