Setting: The study will be conducted in KMP. The community is a resource-limited, densely populated, high HIV/TB disease burden area in Cape Town. The DTHF Tutu Tester Mobile Clinics offer mobile HIV testing days in various locations in KMP. Specifically, there are four high HIV disease burden communities in the district; Philippi (population n=200,803), Crossroads (n=36,043), Gugulethu (n=98,468) and Nyanga (n=57,996). In addition to our well-established relationship with community organisations such as an independent advisory board, we have provided HIV testing services and linkage to treatment from the mobile clinic since 2008 and are currently partnering with the KMP subdistrict health team in providing COVID screening and testing. Given our long-term relationship with and service in the community, our relationships with the Provincial Department of Health, and our experience with the research platforms, it is feasible for us to successfully execute the proposed

research. The mobile clinic team will provide a screening service and SARS-CoV-2 polymerase chain reaction (PCR) testing with the GeneXpert or courier samples to accredited laboratories and rapid testing with the SARS-CoV-2 antibody COVID-19 IgG/IgM Rapid Test Device. Additionally, the mobile clinic team will offer screening for HIV, TB, STI and chronic diseases (e.g. diabetes, hypertension, and obesity).

Design: A cluster randomised controlled study with longitudinal follow up of SARS-CoV-2 infection in 120 households which have newly diagnosed SARS-CoV-2 positive cases. The index cases and their household contacts will be invited to participate in the study after informed consent. Baseline surveys and screening and then weekly screening of HHC will occur (Table 1). These household contacts will be tested at 0, 1, 2, 3 and 4 weeks.

The study design is a type 2 hybrid cluster (household) randomised controlled trial, with outcomes assessed on index patients and their household contacts (Diag 1). 120 consecutively newly diagnosed index patients (GeneXpert SARS-CoV-2 PCR) and up to 8 household contacts will be invited to participate in the trial as part of the prospective observational study evaluating transmission and symptoms. After completing consent, households will be randomised in a 1:1 ratio in blocks of 10 (60 households per group; 360 patient and household contacts per group).

Diagram 1: Study flow

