Written material	Extensive content available online. Limited content available as pamphlets and WhatsApps. No systematic distribution of WhatsApp messaging.	Printed copies of PACK Home Volume 1 (Be coronavirus safe) and Volume 2 (COVID-19 Caring at home).	Printed copies of PACK Home Volume 1 and 2. WhatsApp optimised versions of content delivered daily.
Community Health Worker visits	Mainly alongside chronic medication delivery.	Mainly alongside chronic medication delivery.	Additional one off household assessment to establish relationship at baseline.
Equipment	Distributed through drives.	Masks and hand sanitiser at enrolment.	Masks, hand sanitiser, bleach, gloves (to wear when using bleach). Plus on demand during follow-up.
Telephonic and text message support	On demand hotline service.	On demand hotline service	Scheduled support: Active phase (until 14 days after last person in household diagnosed): daily.

			Follow-up phase: 3 times a week for 7-14 days. Close-out: 5 days (to facilitate full integration into usual services).
--	--	--	---

* As of 06/07/2020 patients are considered at risk of severe COVID-19 if they are: 55 years or older or of any age with any one of the following: diabetes, on TB treatment, HIV, kidney disease, hypertension, previous TB, chronic lung disease, on cancer treatment.

Outcomes will be independently assessed by research staff who are also collecting biological samples at 0, 1, 2, 3, and 4 weeks. Baseline surveys will collect information on demographics, COVID-19 symptoms, household tracing information and home/ dwelling characteristics that impact transmission (size, rooms, ventilation, access to safe water, laundry facilities). Patient and household contact surveys will also include standardised measures to assess psychosocial functioning: General Health Questionnaire; UCLA Loneliness Scale and a version of the Brief AIDS-Related Stigma scale adapted for COVID-19. Research staff will complete a checklist documenting uptake of infection control measures at all follow-up contacts (1, 2, 3, 4 weeks). A sample size of 120 households (60 per group; 320 patient and household contacts per group) will provide 80-99% power to detect a 40% reduction in R₀ (2.5 to 1.5) varying the intra-cluster correlation efficient from 0.90 (80%) to 0.05 (99%) (Table 3). Index patients and their contacts will be reimbursed with R150 for their time at the baseline and final study visits.

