Household Contacts (HHC)						
	ICF		x			
	Demography survey		x			
	Symptom check	x		x	x	x
	COVID19 PCR	x		x	x	x
	COVID serology	x		x	x	x
	Follow up surveys	x		x		x

Data Collection and Management: Data will be collected by study staff on handheld devices. Data will be downloaded daily to a central database housed at the DTHF head office. Further details are available in Work Package 5 and the Data Management document.

Statistical Analysis and sample size: We will describe and compare the characteristics and survey outcomes, isolation, and linkages of participants. We calculated the different effect sizes (Table 2). Based on exponential test for comparing hazards, assuming $120*6=720$ subjects, different intraclass correlation coefficients (ICCs) and comparing $R_0=2.5$ (with resulting incidence of 0.208 among 720 subjects) to a reduced R_0 of 0.9 (64% reduction, with resulting incidence of 0.075 among 720 subjects) or 1.25 (50% reduction) or 1.5 (40% reduction).

Table 3: ICC calculations

ICC	Ro 2.5 to 0.9	Ro 2.5 to 1.25	Ro 2.5 to 1.5
	64% reduction	50% reduction	40% reduction
0.05	1.00000	1.00000	0.999944
0.25	1.00000	0.999891	0.991312
0.50	0.999993	0.995042	0.935880
0.75	0.999729	0.972942	0.846222
0.90	0.999033	0.951485	0.792745

The analyses will be determined by the study analysis plan. These analyses include the calculation of the proportion of SARS-CoV-2 positive individuals screened over a 3-month period, the transmissibility of the virus by determining the proportion of SARS-CoV-2 transmitted to household contacts of the identified COVID19 cases over a 4-week period, the period of infectiousness by correlating the time to transmission and clinical symptoms of the index cases, and the symptomatic/asymptomatic ratio among transmitted SARS-CoV-2 in household contacts. The Ro will be determined by both looking at new cases among the population in contact with the index cases and the total population (both in our service and other clinics in the area) diagnosed over time. The main outcome relates to the incidence of new cases of COVID19. These will be analysed using mixed effect Poisson regression models and frailty models to take the clustering by household into account. Both these regression models take the duration of follow up into account. Scores (e.g., GHQ) will be baseline adjusted. Qualitative data will be transcribed, translated and inductively analysed for themes.

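### The power table treats every subject as an infection and ignores the 4-week follow-up limit: for a 40% reduction at ICC 0.90, the stated 79% is about 39–64%

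*SAP*

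**What the plan says.** SAP section 3 (Sample Size Determination, Table 1) and the Protocol (Statistical Analysis and sample size, Table 3) print the same 15 power values. They are introduced as "Based on exponential test for comparing hazards", with 120 × 6 = 720 subjects and five ICCs from 0.05 to 0.90. R0 of 2.5 is compared with 0.9, 1.25 or 1.5. The control value comes "with resulting incidence of 0.208 among 720 subjects", and R0 of 0.9 is given an incidence of 0.075 on the same base. Alpha, follow-up time, expected number of infections and censoring are not stated for this calculation.

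The Protocol's Approach section, after its Table 1, concludes that the design "will provide 80-99% power to detect a 40% reduction" in R0 and gives the size as "60 per group; 320 patient and household contacts per group".

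Other places describe the denominator differently:
- The Schema (Study size) has "n=~6 their household contacts (n=~720").
- Population and Sample has "household contacts of each of the index patients (n=~720"). In both of these, 720 is contacts only.
- The Design text has "60 households per group; 360 patient and household contacts per group", which makes 720 patients plus contacts. The SAP randomisation paragraph agrees with it.

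Contacts are tested to week 4, and SAP 7.1 plans "exponential shared frailty models taking the clustering by household into account and allowing for censoring".

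**The concern.** In a time-to-infection comparison, information comes from infections, not from people enrolled. A contact still uninfected at week 4 is censored and adds little. Power near 80% at an ICC of 0.90 is surprisingly high for 120 households, because the design effect at that ICC is 5.5.

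The table and the power sentence are the only justification given for 120 households, and they bear on the Aim 2 primary endpoint. If the power is overstated, a null result would be read as evidence against a 40% reduction that the trial may have had an even chance, or less, of detecting.

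**Working it through.** **1. Reproduce the plan's figures.** Effective N = 720/(1 + 5 × ICC) = 576, 320, 205.7, 151.6 and 130.9. Use an exponential hazard-difference test with no censoring and two-sided 0.05 (inferred, because the plan does not state it), with n = half the effective N:

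power = Φ(|h1 − h2| / √(h1²/n + h2²/n) − 1.96)

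For 2.5 vs 1.5 at ICC 0.90, with N entered as 131 and n = 65.5: 1.0/√((6.25 + 2.25)/65.5) = 2.776, and Φ(2.776 − 1.96) = 0.7927, as printed. With N entered as 576, 320, 206, 151 and 131, all ten cells of the 40% and 50% columns match to every printed digit. The 64% column matches with a pooled-null variance (0.999993, 0.999729 and 0.999033 at ICC 0.50, 0.75 and 0.90).

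The variance h²/n is that of a hazard estimated from n *events*. If both hazards are multiplied by the same constant, it cancels. Only the ratio of the R0 values matters, so 0.208, 0.075 and the 4-week limit never enter.

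**2. Where 0.208 comes from.** 60 × 2.5 = 150 and 150/720 = 0.208; 60 × 0.9 = 54 and 54/720 = 0.075. Each is one arm's infections over both arms' subjects. Per arm they are 150/360 = 0.417 and 54/360 = 0.15. If the six people include the index patient, five are at risk: 2.5/5 = 0.50, with 300 contacts per arm.

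**3. Infections expected and needed.** R0 of 2.5 vs 1.5 gives 60 × 2.5 + 60 × 1.5 = 240. On the hazard-ratio scale the count is about 249 (control risk 0.417) to 252 (control risk 0.50). For a hazard ratio of 0.6 with 80% power, 4 × (1.96 + 0.84)²/(ln 0.6)² ≈ 120 infections are needed before clustering. With the design effect that is 120 × 1.25 = 150 at ICC 0.05, and about 662 at ICC 0.90 (unrounded 120.3 × 5.5).

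**4. Recomputed power, 40% reduction.**

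Var(log HR) = (1/(n·p1) + 1/(n·p2)) × (1 + (m − 1) × ICC)

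Here n is contacts per arm, m is contacts per household, hazards are −ln(1 − risk), and the test is two-sided 0.05. Example: p1 = 0.417, HR 0.6, so p2 = 1 − (1 − 0.417)^0.6 = 0.276. At ICC 0.90 the standard error is √(0.01672 × 5.5) = 0.303, and Φ(0.511/0.303 − 1.96) = 0.39.

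| Reading | ICC 0.05 | 0.25 | 0.50 | 0.75 | 0.90 | 80% holds up to ICC |
|---|---|---|---|---|---|---|
| Stated in the plan | 0.9999 | 0.991 | 0.936 | 0.846 | 0.793 | – |
| 0.417 vs 0.25 (risk ratio 0.6), 360 per arm | 0.99 | 0.88 | 0.71 | 0.58 | 0.52 | about 0.37 |
| 0.417 vs 0.276 (HR 0.6), 360 per arm | 0.94 | 0.75 | 0.56 | 0.44 | 0.39 | about 0.20 |
| 0.50 vs 0.30 (risk ratio 0.6), 300 per arm | 0.995 | 0.94 | 0.82 | 0.70 | 0.64 | about 0.54 |
| 0.50 vs 0.34 (HR 0.6), 300 per arm | 0.95 | 0.80 | 0.63 | 0.51 | 0.46 | about 0.25 |
| 0.208 as control-arm risk, risk ratio 0.6 | 0.76 | 0.51 | 0.35 | 0.28 | 0.24 | – |
| 0.208 as control-arm risk, HR 0.6 | 0.69 | 0.45 | 0.31 | 0.24 | 0.21 | – |

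**5. Cross-check.** A beta-binomial simulation (60 vs 60 households, cluster-level t-test, 4,000 runs) gave 0.53, 0.39, 0.66 and 0.46 at ICC 0.90 for the four per-arm rows, and 0.99, 0.94, 0.996 and 0.95 at ICC 0.05.

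**6. Larger effects at ICC 0.90.** The 64% column states 0.999. Per-arm risks 0.417 vs 0.15 give 0.90, and the printed 0.208 vs 0.075 taken literally give 0.55 (0.61 by simulation). The 50% column states 0.951. Per-arm 0.417 vs 0.208 gives 0.71, and 0.50 vs 0.25 gives 0.83.

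**The case against.** - **The no-censoring assumption is inferred.** This is true, as it is for alpha, and the match needs mixed rounding (205.7 up, 151.6 down) and a different variance for one column. Even so, agreement to every printed digit is hard to attribute to chance.
- **The per-arm risks are derived.** They treat R0 as infections per household over 4 weeks, and the Protocol says R0 will also draw on the wider population. With a risk ratio of 0.6, 80% power at ICC 0.90 would be reached at a control risk of about 0.61. R0 of 2.5 shared among five or six people gives 0.50 or 0.417. With a hazard ratio of 0.6, power is still only 0.61 at an assumed control risk of 0.70.
- **ICC 0.90 is the edge of a sensitivity grid.** This point stands in part. At ICC 0.05 the four per-arm readings keep at least 0.94, and larger effects lose less. But the plan names no expected ICC, and the Protocol's sentence claims the range up to 0.90.
- **The replacement figures are not a fitted frailty model.** Correct. They are approximations that count infections, and simulation agrees with them. The 662 needed also comes from a log-hazard formula. On a log-hazard (Schoenfeld) calculation the plan's 720 events would give 0.832, not 0.793. The shortfall from about 240–250 infections is far larger than that difference.
- **Nothing else in the SAP uses this power.** There is no interim analysis or stopping rule, and a confidence interval would carry much of the interpretation. That limits the consequences but does not make the published power claim right.
- **The 720/360/320 conflict is a separate matter.** It is, but an index patient cannot be a new infection, so it fixes the number at risk that any recalculation needs.

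**Conclusion.** The concern holds. The table gives the power of a trial in which every effective subject is infected, not of one with about 240 infections and censoring at 4 weeks. For the 40% reduction, the stated 0.793 at ICC 0.90 becomes 0.39–0.64 on the four per-arm readings. The lower end of the Protocol's claim therefore fails on every reading computed here. The upper end largely survives: 0.94–0.995 at ICC 0.05, unless 0.208 is literally the control-arm risk, in which case it is 0.69–0.76. On the per-arm readings, 80% power holds only up to an ICC of about 0.20 to 0.54, depending on effect scale and contacts per household.

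These figures assume two-sided 0.05, R0 read as household infections over 4 weeks, no loss to follow-up and no contacts already infected at baseline. Relaxing either of the last two would lower power further.

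**What to change.** Keep the sample size and the analysis model. In both documents:

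1. State whether the 40% reduction is a risk ratio or a hazard ratio. The planned frailty model estimates a hazard ratio.
2. State the 4-week infection risk in each arm, over that arm's household contacts at risk.
3. Name the ICC the plan expects, and keep the grid as sensitivity.
4. Recompute SAP Table 1 and Protocol Table 3 from expected infections, with censoring at 4 weeks and the design effect. State alpha and sidedness.
5. Replace the power range in the Protocol's Approach section with the recomputed one.
6. Reconcile 720 as contacts only with 720 as patients plus contacts, and 320 with 360 per group.

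The figures above show the size of the change under each reading. They should not be inserted before items 1 to 3 are settled. The cost is one table, one sentence on assumptions and one power sentence, and a less favourable stated power.
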